7.2 Secondary Efficacy Analyses

7.2.1 Important secondary endpoints

Preeclampsia is an important secondary endpoint in this study. This analysis will be conducted in the ITT population.

The frequency of occurrence of preeclampsia will be presented as N and percent of the total study population and by treatment group. To obtain the relative risk and 95% CI of the occurrence of the secondary endpoints, log-binomial regression models will be used. If the log-binomial model does not converge, the log-Poisson models will be used instead(27). The inclusion of covariates will be considered in the same manner as for the primary endpoint.

The time-to-occurrence of preeclampsia will be compared by treatment using Kaplan-Meier curves, with a p-value from Log-rank test reported.

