3.4 Randomisation (Interventions: Investigational and placebo therapy)

This study will employ a randomised, patient and investigator-blinded, multi-centre, parallel-group, placebo controlled design to assess efficacy, safety and tolerability of Low dose aspirin for preventing intrauterine growth restriction and preeclampsia in sickle cell pregnancy (PIPSICKLE).

At the baseline visit, a pregnant woman who is referred or is found to have sickle cell disease (HbSS or HbSC) on routine haemoglobin genotype testing, meets the eligibility criteria and gives informed consent will be enrolled and randomised to one of the two treatments groups (Blinded)

Randomisation and allocation concealment will be done with the use of a web-based randomisation software known as ‘Sealed envelope’ in a 1:1 ratio in blocks stratified according to centre. Only an unblinded pharmacist will be aware of the actual codes and the pharmacist will not be in contact with any of the study participants or investigators.

A total of 476 eligible pregnant HbSS and HbSC women will be randomly assigned to either group.

Those in the LDA group will receive 100mg aspirin daily while those in the placebo group will receive a tablet that looks like the active drug in terms of diameter, thickness and colour.

The drugs will be started between 12 and 28 weeks’ gestation and continued till 36 weeks or delivery, whichever comes earlier.

The study drugs will be prepared in sachets and dispensed in 2 weekly doses (*3 weeks dosage at enrollment*). The women will be sent daily reminders by text message, questioned on compliance at each visit and asked to bring in their used sachets for sighting. All the women will be followed from enrollment till delivery.

The study drugs will be packed in boxes labelled with codes and each box will have sufficient study drugs for one patient for 24 weeks with 4 extra weeks’ worth of drug in case the patient loses some pills. The drug boxes will be delivered to each centre in batches of 8 (4) and 4 (2) more boxes will be sent to the centre whenever a message is received from the centre that there are 4 boxes left.

In the unlikely event that a woman loses all her drugs, the unblinded pharmacist will be asked to label another batch for the woman, based on the code list that she holds. If all the relevant drugs have been used up, the trial pharmaceutical company Emzor Pharmaceutical Ltd, will be asked to produce a new pack of study (investigational or control) drug.

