4.1 Inclusion criteria

- Age 18 years and above
- Singleton fetus
- Hb genotypes are Haemoglobin SS or SC.
- 12-28 weeks gestation at recruitment, estimated from the last menstrual period or by an early ultrasound scan.

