5.5 Study Completion visit (Pregnancy loss or delivery)

A participant will be considered to have completed the study once there is a pregnancy loss or delivery at any time after randomisation and all relevant data is captured into the appropriate study completion CRF.

The following steps will be taken at the end of study visit

- ❖ Physical examination
- ❖ Evaluate compliance & ADE
- ❖ Complete all relevant documents
- ❖ Complete delivery e-CRF (*at delivery- Appendix viii*) and end of study visit e-CRF at completion of all study visits and data entry (*Appendix ix*) and other relevant source documents.

- ❖ Counselling and necessary referral (e.g Postpartum and family planning clinics)

Tables below lists all of the assessments and indicates with an “X” the visits when they are performed. All data obtained from these assessments must be supported in the patient’s source documentation. The Table indicates which data are entered into the database (D) or remain in source documents only (S) or both (SD).

Assessments that generate data for database entry and which are recorded on CRFs are listed using the CRF name (Enrollment, Visit, Study completion). Assessments that are transferred to the database electronically (e.g. laboratory data) are listed by test name.

Table 1: Study Visit Schedule

	Pre-treatment	Treatment (Enrollment and follow-up)																			Delivery			
Study Visit	0	1	2	3	4	5	6	7	8	9	10	11	12	13	14	15	16	17	18	19	20	21		
GA in weeks	6-11	12	14	16	18	20	22	24	26	28	29	30	31	32	33	34	35	36	37	38	39	40		
Screening	X	X	X	X	X	X	X	X	X															
Enrollment		X	X	X	X	X	X	X	X	X														
Follow-up			X	X	X	X	X	X	X	X	X	X	X	X	X	X	X	X	X	X	X	X	X	
End of study				X	X	X	X	X	X	X	X	X	X	X	X	X	X	X	X	X	X	X	X	

Table 2: Assessment schedule for study participants

Phase	Pre-Treatment	Treatment (Enrollment and follow-up)																	Delivery			
Study visit	0	1	2	3	4	5	6	7	8	9	10	11	12	13	14	15	16	17	18	19	20	21
GA in weeks	6-11	12	14	16	18	20	22	24	26	28	29	30	31	32	33	34	35	36	37	38	39	40
Inclusion/exclusion criteria (S)	X	X	X	X	X	X	X	X	X													
Written informed consent (S)	X	X	X	X	X	X	X	X	X													
Demographics/ PMH (SD)	X	X	X	X	X	X	X	X	X													
Concomitant medication (SD)	X	X	X	X	X	X	X	X	X	X	X	X	X	X	X	X	X	X	X	X	X	X
Body weight (SD)	X	X	X	X	X	X	X	X	X	X	X	X	X	X	X	X	X	X	X	X	X	X
Physical examination (SD)	X	X	X	X	X	X	X	X	X	X	X	X	X	X	X	X	X	X	X	X	X	X
Laboratory (SD) Hb +Urinalysis	X	X	X	X	X	X	X	X	X	X	X	X	X	X	X	X	X	X	X	X	X	X

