2.2 Endpoints

Primary

1. IUGR, perinatal death or miscarriage as a composite outcome

The occurrence of either IUGR, perinatal death or miscarriage will be the primary outcome.

IUGR will be defined as birthweight <10th centile for gestational age on the INTERGROWTH-21st birthweight charts, which is based on a healthy reference cohort from multiple countries, including Kenya(16). IUGR based on the Oken charts from a US national reference(17) maybe presented in sensitivity. A perinatal death refers to the death of a fetus after the age of viability (≥ 28 weeks' EGA), at delivery, or within the first week of life. A miscarriage refers to pregnancy, loss the death of a fetus before the age of viability (< 28 weeks' EGA). All participants will do an ultrasound scan at 20 weeks to estimate the gestational age of the pregnancy. Analysis will be by intention to treat.

Hypothesis:

1. We expect a 50% lower incidence of IUGR, perinatal death or miscarriage in the LDA (intervention) group compared to the placebo (control) group.

Secondary

1. The incidence of preeclampsia. Preeclampsia will be diagnosed based on ISSHP classification(18) if there is development of hypertension (either systolic blood pressure ≥ 140 mm Hg or diastolic blood pressure ≥ 90 mm Hg on two occasions at least 4 h apart) after 20 weeks gestation plus one of the following: proteinuria, thrombocytopenia, or any multisystem complication. Proteinuria will be defined as a dipstick test with 1+ proteinuria (≥ 30 mg dl $^{-1}$) on two occasions at least 4 hours apart, without any evidence of a urinary tract infection, or 2+ proteinuria or more on dipstick, or urinary protein creatinine ration >300 mg/g. Thrombocytopenia will be defined as a platelet count of $<100,000$ mm $^{-3}$.
2. The incidence of preterm delivery, defined as delivery at <37 weeks' EGA.
3. The incidence of:
 - a. Maternal death
 - b. Perinatal death
4. Number of sickle cell crises
5. Need for blood transfusion – identified based on whether the participant received a blood transfusion or not
6. Incidence of complications such as:
 - a. Urinary tract infection (UTI),
 - b. Lower Respiratory Tract Infection,
 - c. Acute chest syndrome,
 - d. retained placenta,
 - e. placental abruption; and
7. Incidence of potential adverse effects such as:
 - a. vaginal bleeding,
 - b. epigastric pain, and
 - c. heartburn

Analysis will be by intention to treat.

3 Study Methods

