Preterm delivery	Continuous variable, measured in weeks. The lower limit of acceptable range is 12 weeks. The usual upper limit is 44 weeks, beyond which baby is unlikely to have survived. 
 ▪ A secondary endpoint
Maternal mortality	Binary variable (0, 1). Defined as any death of a woman during the study (during pregnancy and puerperium) 
 ▪ A secondary endpoint
Haemoglobin F	Categorical variable (<2%, 2 – 10%, >10%), measured in percent. Calculated

Variable	Description
fraction	from continuous HbF fraction 
 ▪ A baseline covariate ▪ Levels of HbF fraction are related to clinical outcomes among people with sickle cell disease(19)
Haemoglobin A2 fraction	Categorical variable (<3.5%, ≥3.5%), measured in percent. Calculated from continuous Hb A2 fraction 
 ▪ A baseline covariate ▪ Levels of HbA2 fraction are suggestive of β thalassemia carrier status(20)
Follow-up duration	Continuous variable, measured in days. Calculated as the difference between the date of randomization to the date of delivery or miscarriage.

4 Sample Size

Assuming an incidence of intrauterine growth restriction (IUGR) of 20% in sickle cell disease(21) and expecting a 50% IUGR reduction with the use of LDA as detected by Bujold et al(22), we calculated that 198 women per group would be required to have a 90% power of detecting a decrease in IUGR at the 5% significance level, with a total of 396, using the formula for proportions in superiority parallel trial(23). Allowing for 20% attrition, this would become 476 in total.

5 General Analysis Considerations

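### The Kaplan-Meier analysis of preeclampsia has no rule for the end of pregnancy; the default censors at delivery, so the late curve overstates incidence

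*SAP*

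**What the plan says.** SAP 7.2.1 plans two analyses of preeclampsia in the intention-to-treat population.

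- **Proportions.** "The frequency of occurrence of preeclampsia will be presented as N and percent of the total study population and by treatment group". For the effect, "To obtain the relative risk and 95% CI of the occurrence of the secondary endpoints, log-binomial regression models will be used".
- **Time to event.** "The time-to-occurrence of preeclampsia will be compared by treatment using Kaplan-Meier curves, with a p-value from Log-rank test reported". This is the only sentence on it. It states no time origin, censoring rule or competing-event rule.

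Other places bear on how that sentence would be carried out.

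- **End of follow-up.** Protocol 5.5: "A participant will be considered to have completed the study once there is a pregnancy loss or delivery at any time after randomisation". The follow-up duration variable in SAP Table 3 is "Calculated as the difference between the date of randomization to the date of delivery or miscarriage", and the crisis analysis in SAP 7.2.3 uses a similar clock as its offset.
- **Entry.** Protocol 4.1 admits women at "12-28 weeks gestation at recruitment, estimated from the last menstrual period or by an early ultrasound scan".
- **Start of risk.** SAP 2.2 requires hypertension "after 20 weeks gestation plus one of the following: proteinuria, thrombocytopenia, or any multisystem complication". It sets no upper time limit.
- **Postpartum.** SAP 3.4 Table 1 and SAP 6.1 list a visit after delivery, up to six weeks postpartum.

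**The concern.** Kaplan-Meier treats a censored woman as still able to have the event later, at the same rate as those who remain. That is reasonable for a woman lost to follow-up. It is not reasonable for a woman who has delivered or miscarried, if only onset during pregnancy counts. Almost every woman without preeclampsia leaves the risk set in this way, so the censoring is heavy and concentrated at the end of the curve.

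Two things follow. The curve for a title endpoint would end well above the percentage printed in Table shell 3, and a reader could take the wrong absolute risk from it. Also, preterm delivery and pregnancy loss are themselves outcomes of this trial. If aspirin shifts them, the log-rank p-value and the risk ratio answer different questions, and the SAP does not say so.

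**Working it through.** **Plan's own figure.** There is none to reproduce. The documents give no preeclampsia rate, hazard ratio or distribution of delivery times. Every rate below is an assumption; only the entry window, the 20-week start of risk and 238 women per arm come from the documents.

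**1. Direction.** Let h_P be the weekly preeclampsia hazard and h_E the hazard of pregnancy ending without it.

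- One minus Kaplan-Meier, censoring at end of pregnancy: 1 − exp(−∫h_P).
- Cumulative incidence: ∫ h_P(u) · exp(−∫(h_P + h_E)) du, with the inner integral taken up to u.

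The two are equal only when h_E = 0. Otherwise the first is larger, whatever the rates.

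**2. Size by gestational age.** Assume h_P = 0.0015 per week at 20–28 weeks, 0.006 at 28–34 and 0.02 from 34. Assume h_E = 0.9·exp(0.75·(GA − 39.5)), capped at 3. This gives a median delivery of about 38.8 weeks. The Kaplan-Meier column can be checked by hand; the cumulative incidence is by numerical integration.

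| GA (weeks) | ∫h_P | 1 − KM | Cumulative incidence | Ratio |
|---|---|---|---|---|
| 37 | 8×0.0015 + 6×0.006 + 3×0.02 = 0.108 | 10.2% | 9.8% | 1.04 |
| 38 | 0.128 | 12.0% | 11.2% | 1.07 |
| 40.9 | 0.186 | 17.0% | 12.8% | 1.33 |

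Only about 2.7% of women are still at risk at 40.9 weeks. With every delivery one week earlier and the same h_P, cumulative incidence at 40.9 weeks falls to 11.1%, while one minus Kaplan-Meier stays at 17.0%. The curve cannot show that change.

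**3. Size on time from randomisation.** This simulation uses different assumptions: entry uniform over 12–28 weeks; cumulative preeclampsia hazard proportional to ((GA − 20)/20)³; delivery about N(38, 2.2) weeks; miscarriage probability 0.05 × (28 − entry week)/8. Cells show cumulative incidence versus one minus Kaplan-Meier.

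| Assumed overall incidence | 16 weeks | 20 weeks | 26 weeks |
|---|---|---|---|
| 5% | 3.2% v 3.8% | 4.2% v 6.1% | 4.9% v 9.9% |
| 10% | 6.3% v 7.6% | 8.2% v 11.7% | 9.9% v 20.3% |
| 20% | 12.8% v 15.2% | 16.8% v 23.4% | 19.8% v 37.7% |
| 30% | 19.6% v 23.0% | 25.6% v 34.7% | 29.7% v 53.4% |

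The ratio is about 1.4 at 20 weeks (for example 23.4/16.8 = 1.39) and 1.8 to 2.1 at 26 weeks. In a re-run of the 20% case, about 30% of women were still at risk at 20 weeks and about 4% at 26 weeks. On this clock the gap is therefore not confined to the sparse tail.

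**4. Effect of entry at 12–28 weeks.** On time from randomisation everyone enters at zero, so there is no left truncation. On gestational age, ignoring delayed entry lowers one minus Kaplan-Meier at 40 weeks by 0.1 to 0.3 points (for example 27.1% to 26.9%, against a cumulative incidence of 19.3%).

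**5. Comparison of arms.** Same model as step 3, 238 per arm, 2,000 trials per setting, placebo risk about 11% to 34%. The hazard ratio (HR) ranges cover both time scales. Disagreement means that the test of proportions and the log-rank test (time from randomisation) differ on significance at 5%.

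| Assumed aspirin effect | RR | Ratio of 1 − KM at 40 weeks | Log-rank HR | Disagreement |
|---|---|---|---|---|
| Hazard halved only | 0.52–0.56 | 0.52–0.57 | 0.50–0.52 | 2–7% |
| No effect on hazard; delivery 1 week later, miscarriage halved | 1.15–1.19 | 1.00–1.01 | 1.00–1.05 | 6–21% |
| Hazard halved; delivery 1 week later, miscarriage halved | 0.61–0.66 | 0.52–0.58 | 0.50–0.54 | 16–19% |

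With no effect of any kind, all tests reject in about 5% of trials.

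**The case against.** The strongest reply is that the SAP contains no wrong rule. It does not say that delivery is censored, and no Kaplan-Meier incidence estimate is planned. Absolute risks come from the N and percent by arm, and the effect from the risk ratio. The curve is a supplement to a secondary endpoint. This stands, and it makes the fault one of under-specification. It does not remove the fault, because censoring at the end of pregnancy is what standard routines do with the only follow-up clock that the SAP defines.

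Three stronger readings are tempting, and the documents do not support them.

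- **That staggered entry inflates the curves.** It does not (step 4). The event-free weeks of a woman enrolled at 12 weeks are a flat stretch, balanced by randomisation.
- **That the curves contradict the risk ratio.** If aspirin acts only on the preeclampsia hazard, the measures agree closely. Materially different answers need an effect on delivery timing or pregnancy loss, and the documents give no size for one.
- **That the log-rank test is invalid.** It holds its level and properly compares cause-specific hazards.

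Two further points stand. Before about 37 to 38 weeks the gap on the gestational-age scale is small under the hazards of step 2. And delivery ends the risk only if postpartum onset is excluded, which the SAP leaves open. Loss to follow-up remains ordinary censoring.

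**Conclusion.** The point holds as a low-cost improvement. SAP 7.2.1 leaves the time scale and the handling of the end of pregnancy unstated, and the default reading gives curves that overstate cumulative incidence and do not match the percentages beside them. The direction follows from the formulas if only onset before the end of pregnancy counts. The size rests on assumed rates: about 4% relative overstatement at 37 weeks and about a third at 40.9 weeks in one illustration, and about 1.4-fold at 20 weeks from randomisation, rising to about 2-fold at 26 weeks, in another.

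A reader might infer that the comparison of arms is biased. That goes too far: the log-rank p-value is sound for its own question and needs only a label. The primary composite and the preeclampsia risk ratio are untouched.

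**What to change.** Replace the Kaplan-Meier sentence in SAP 7.2.1 with wording to this effect:

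- Cumulative-incidence (Aalen-Johansen) curves by arm for all randomised women, on time from randomisation. This scale keeps women whose pregnancy ends before 20 weeks. Starting the risk period at 20 weeks would drop them and break the link with the intention-to-treat percentages.
- Delivery, pregnancy loss or maternal death without preeclampsia is a competing event; loss to follow-up is censoring. Apart from such losses, the curve then ends at the reported percentage.
- State whether postpartum onset counts. If it does, women stay at risk after delivery until a stated limit, and delivery is not a competing event.
- State how the onset date is derived, because the delivery form in the protocol appendix has a tick item for preeclampsia but no date.
- Label the log-rank p-value as a comparison of cause-specific hazards, and name the risk ratio as the main estimate. Gray's test would address a different estimand and is a choice, not a correction.

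The cost is a few sentences and standard Stata or R routines. The downside is a slightly less familiar plot.

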7.2.2 Other Secondary Endpoints

This analysis will be conducted in the ITT population. The relevant endpoints include preterm delivery, maternal death, perinatal death, need for blood transfusion, and the incidence of complications such as UTI.

The frequency of occurrence of the categorical endpoints will be presented as N and percent of the total study population and by treatment group.

To obtain the relative risk and 95% CI of the occurrence of the secondary endpoints, log-binomial regression models will be used. If the log-binomial model does not converge, the log-Poisson models will be used instead(27). The inclusion of covariates will be considered in the same manner as for the primary endpoint.

Table shell 3: Secondary outcomes

Outcome	Level	LDA, n(%)	Placebo, n(%)	Risk ratio	Confidence intervals	P-value
Preeclampsia	Yes					
	No					
Preterm delivery	Yes					
	No					
Maternal death	Yes					
	No					
Need for blood transfusion	Yes					
	No					
Incidence of UTI	Yes					
	No					
Pneumonia	Yes					
	No					
Sepsis	Yes					
	No					
Stillbirth	Yes					
	No					

7.2.3 Number of crises

The number of crises is a count variable and will be analyzed in the ITT population. Crises of the same type that occur within 28 days of one another will be regarded as a single event in line with the clinical convention in Nigeria(39).

For the total study population and each treatment group, N, mean, standard deviation (SD), median, interquartile range, minimum and maximum will summarize count variables as appropriate based on its distribution and other statistical considerations.

To obtain the rate ratio and 95% CI of the number of crises, Poisson regression models or its variant will be used with the duration of intervention (the number of weeks between study enrolment and end of pregnancy) as the offset term.

Table shell 4: Sickle cell crises

Outcome	Value	LDA	Placebo	IRR	Confidence intervals	P-value
Number of sickle cell crises	Mean (SD)					
Follow-up time, weeks	Mean (SD)					
Types of sickle cell crisis						
Vaso-occlusive	Mean (SD)					
Hemolytic	Mean (SD)					
Sequestration	Mean (SD)					
Acute Chest Syndrome (ACS)	Mean (SD)					
Severe anemia	Mean (SD)					
Others	Mean (SD)					

8 Safety Analyses

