5.2 Analysis Populations

5.2.1 Intention to Treat (ITT) population

- The intention to treat population refers to all subjects who were randomised. Following the intention-to-treat principle, patients will be analysed according to the treatment they were assigned to at randomization.

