5.4 Missing Data

No imputation of endpoints will be done in the main analysis. Throughout, the denominator for each analysis will be reported to be transparent wherever there is missing data. For outcomes missing in <5% of those for whom it is expected, missing data will be ignored as imputation is unlikely to improve the precision or prevent bias(24). This approach is known as a *complete-case intention-to-treat* approach(25).

For outcomes missing in ≥5% of participants for whom it is expected, supplementary tables comparing baseline characteristics in those with and without the missing outcome will be reported. In addition, multiple imputation or inverse probability of treatment weighting will be considered, and results compared with the complete case analysis.

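### The crisis-rate model defines no time at risk for women whose follow-up stops before a known end of pregnancy

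*SAP*

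**What the plan says.** SAP 7.2.3 places the crisis count in the ITT population, and SAP 5.2.1 defines that population without exclusions: "The intention to treat population refers to all subjects who were randomised". The model is left partly open: "Poisson regression models or its variant will be used". Exposure time is then brought in by a clause that reads "with the duration of intervention (the number of weeks between study enrolment and end of pregnancy) as the offset term". The result is a rate ratio, shown in the IRR column of Table shell 4.

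SAP 3.4, Table 3 has a matching follow-up variable. Its type and unit are given as "Continuous variable, measured in days", and its start and end are fixed by the definition "Calculated as the difference between the date of randomization to the date of delivery or miscarriage". Neither place gives a censoring date for a woman who is lost or withdrawn while still pregnant.

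On missing data, SAP 5.4 says "No imputation of endpoints will be done in the main analysis". For outcomes missing in 5% or more of participants, it commits to tables of baseline characteristics and adds that "multiple imputation or inverse probability of treatment weighting will be considered, and results compared with the complete case analysis". It does not mention a missing exposure time.

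SAP section 4 provides for losses: "Allowing for 20% attrition, this would become 476 in total".

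The Protocol glossary says that no further assessments are planned once a woman is prematurely withdrawn. Protocol 6.1 makes stopping study drug a reason for mandatory withdrawal. Protocol 7.7 says that women who stop study drug continue to be followed.

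**The concern.** A rate model needs two quantities per woman: the crises counted, and the time over which they could have been counted. The SAP ties the second to an event that will not be known for everyone. A woman seen for two months and then lost has a valid count and a valid observed time, but no offset under the stated rule.

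At stake is a listed secondary endpoint (SAP 2.2, item 4). Omitting such women discards usable person-time and departs from the declared population. Giving them time to a delivery date traced later lowers their apparent crisis rate. If early loss differs by arm in a way related to crises, either error could move the rate ratio. The open choice of count model adds a smaller point, because plain Poisson with model-based standard errors remains allowed.

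**Working it through.** **No document figure to reproduce for crises.** The documents give no crisis rate, dispersion, expected rate ratio or power for this endpoint. Only the attrition allowance can be traced:

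- 2 × 198 = 396, and 396 × 1.2 = 475.2, taken as 476.
- Allowance for loss: 476 − 396 = 80 women, and 80/476 = 16.8%, about 1 in 6.

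**What the stated rule does to a woman whose follow-up stops early**

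| Situation | Offset under SAP 7.2.3 | Consequence |
|---|---|---|
| Pregnancy end known, crises reported throughout | Defined | Correct |
| Pregnancy end unknown | Missing | Leaves a complete-case fit; her crises and weeks are lost |
| Pregnancy end traced, crisis reporting stopped earlier | Defined but too long | Rate understated |

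Illustration of the last row, with hypothetical times: crises reported for 8 weeks, delivery traced to 24 weeks after enrolment. The offset credits 24 weeks, so her rate is understated by a factor of 24/8 = 3.

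**Cost of dropping women under random loss (simulation; all rates assumed).** Inputs: 238 women per arm; enrolment uniform over 12 to 28 weeks; delivery around 38 weeks; control rate about 1 crisis per 18 weeks; gamma-Poisson counts with variance/mean about 2; true rate ratio 0.7; 20% lost at random; robust standard errors; 600 runs.

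| Analysis | Mean estimated rate ratio | Mean SE (log scale) | Power |
|---|---|---|---|
| Lost women dropped | 0.707 | 0.154 | 61% |
| Lost women kept, log(observed weeks) | 0.699 | 0.145 | 69% |

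Both estimates centre on 0.7, so random loss gives no bias here. The Monte Carlo error of each power is about √(0.61 × 0.39/600) = 2 percentage points. As a cross-check, Φ(|ln 0.7|/SE − 1.96) with |ln 0.7| = 0.357 gives:

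- dropped: Φ(0.357/0.154 − 1.96) = Φ(0.36) = 64%;
- kept: Φ(0.357/0.145 − 1.96) = Φ(0.50) = 69%.

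The gain is therefore roughly 5 to 8 points. The simulated 20% loss is slightly more than the 16.8% above.

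**Choice of count model (dispersion assumed).** If variance/mean is φ, a plain Poisson standard error is too small by √φ, and a nominal two-sided 5% test has false-positive rate 2 × [1 − Φ(1.96/√φ)]:

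- φ = 1: 2 × [1 − Φ(1.96)] = 5%
- φ = 1.5: 2 × [1 − Φ(1.600)] = 11%
- φ = 2: 2 × [1 − Φ(1.386)] = 17%

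Simulation agreed: plain Poisson rejected a true null in 4% of runs at φ of about 1 and 16% at about 2. Robust or quasi-Poisson variance held it to between 4% and 6%.

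**Units.** Table 3 uses days and 7.2.3 uses weeks. With a logged offset, the factor of 7 only shifts the intercept and leaves the rate ratio unchanged. One unit is still tidier.

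**The case against.** The SAP nowhere says that lost women are excluded; it says ITT. Protocol 5.1 and 6.2 require active tracing with at least three contact attempts, and files stay open until close-out, so some pregnancy end dates will be recovered. SAP 5.4 has provisions for missing outcomes. All of this is fair, and it means that the number of women affected cannot be stated. It does not remove the gap. Tracing a delivery date without crisis information turns a missing offset into an overlong one. SAP 5.4 concerns endpoints, and its main analysis is complete-case, so at best it confirms the omission.

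Four stronger readings are tempting, and the documents do not support them.

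- *One woman in five will be dropped.* The 20% is a sample-size allowance, worth 80 of 476 by the SAP's own arithmetic. It is not a count of missing end dates.
- *The rate ratio will be biased.* This needs loss related to both crises and arm. No evidence of that is given, and random loss produced no bias above.
- *The offset is on the wrong scale.* Read literally, raw weeks in a log-link model would multiply the expected count by exp(24 − 8) = exp(16), about 8.9 million, between 8 and 24 weeks, instead of by 3. But the rate-ratio wording and the IRR column show that a rate model is meant, so this is a missing word. SAP section 11 also provides for an independent check of the code.
- *The confidence intervals will be too narrow.* The wording already permits a negative binomial or robust variant, no dispersion is given, and counting same-type crises within 28 days as one may reduce clustering. What stands is that no variant, selection rule or variance estimator is named; the site-clustered errors of SAP 7.1 are not carried into 7.2.3.

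**Conclusion.** The point holds for time at risk. As written, exposure ends only at end of pregnancy, so a woman whose follow-up stops earlier either has no offset or may be credited with unobserved time. The size is modest: a loss of roughly 5 to 8 points of power at a rate ratio of 0.7, on assumed rates and 20% random loss. The true number of women affected is unknown, and bias is a possibility only.

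Model choice is a secondary matter of pre-specification. If plain Poisson were used, the false-positive rate would run from 5% with no overdispersion to 17% at twice Poisson variance, and the documents do not say where in that range the data will lie. This is a worthwhile, inexpensive clarification of a secondary endpoint and does not touch the primary analysis.

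**What to change.** Replace the model sentence in SAP 7.2.3, and align Table 3, to say that:

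- the offset is the logarithm of weeks from randomisation to the earlier of end of pregnancy and the last visit at which crises were ascertained, in one unit throughout;
- all randomised women with any follow-up time are included, and those with none are counted by arm;
- the model is negative binomial, or Poisson with robust standard errors, with one chosen now, stating whether the site clustering of 7.1 applies.

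The label for the offset should also be corrected. It is called the duration of intervention, but Protocol 3.4 ends study drug at 36 weeks or at an earlier delivery, whereas the offset runs to end of pregnancy.

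Protocol 6.1 and 7.7 contradict each other on women who stop study drug. They must be reconciled, because they determine how long these women are observed.

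The cost is SAP wording and a short derivation. Visit dates are already on the follow-up form (Appendix 07). The End of Study form cannot supply the date: it has no last-contact field, and for lost women it is completed only at close-out. Appendix 07 lists crisis type next to the reason for an unscheduled visit, so the SAP should also say which visits count as ascertaining crises. The new rule still assumes that stopping follow-up is unrelated to later crises, so early stopping should be reported by arm.
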